11.4.2. Clinical Severity and Clinical Course of RSV Infection

All data from PRO questionnaires for the assessment of the subject's severity of RSV symptoms, health and functioning, and HRQOL (see Section 9.2.2) will be summarized descriptively by treatment group.

More details regarding the analysis of these data will be described in the SAP.

11.4.3. Viral Sequencing

The sequencing results of the F-gene (and other regions of the RSV genome at the request of the protocol virologist) and changes from baseline will be summarized. Sequencing results may be presented in a separate report.

11.5. Pharmacokinetic Analyses

Population pharmacokinetic analysis of concentration-time data of JNJ-53718678 will be performed using nonlinear mixed-effects modelling. An updated popPK model will be developed with the current adult data combined with those of selected Phase 1 studies to support a relevant structural model. Available subject characteristics (demographics, laboratory variables, etc.) will be tested as potential covariates affecting pharmacokinetic parameters. This updated model will be used for the final pharmacokinetic parameters estimation for each subject with available data. For each dose, descriptive statistics including arithmetic mean, SD, coefficient of variation, geometric mean, median, minimum, and maximum of the final pharmacokinetic parameters (AUC, C_{trough} , and possibly C_{max}) will be provided. The pharmacokinetic analyses will be detailed in an analysis plan. Analyses of other analytes (eg, excipients, metabolites) may be performed at the discretion of the sponsor.

A snapshot date for pharmacokinetic samples to be analyzed for the planned interim analysis will be defined. Samples collected before this snapshot date will be analyzed for JNJ-53718678 and included in the popPK analysis. Samples collected after the snapshot date will be analyzed at a later date, and may be included in a popPK re-analysis when they become available after interim analysis database lock.

Subjects will be excluded from the pharmacokinetic analysis if their data do not allow for accurate assessment of the pharmacokinetics (eg, incomplete administration of the study drug; missing information of dosing and sampling times; concentration data not sufficient for pharmacokinetic parameter calculation).

All concentrations below the lowest quantifiable concentration or missing data will be labeled as such in the concentration database. All subjects and samples excluded from the analysis will be clearly documented in the study report.

For each treatment group, descriptive statistics, including arithmetic mean, SD, coefficient of variation, median, minimum, and maximum will be calculated for all individual derived pharmacokinetic parameters including exposure information of JNJ-53718678.

11.6. Other Analyses

Biomarker Analyses

Statistical approaches to explore correlations between clinical outcome, viral load, and biomarkers in blood and mid-turbinate nasal swabs vary and depend on the different data types of the applied technology platforms, as well as on the extent of observed differences among study subjects. Analyses may be conducted at the sponsor's discretion and reported separately from this study.

Pharmacokinetic/Pharmacodynamic Analyses

Relationships of JNJ-53718678 population-derived exposure parameters with selected antiviral activity parameters, clinical outcomes, and safety endpoints will be explored. These relationships will be presented in a tabular and/or graphical display.

Results of pharmacokinetic/pharmacodynamic analyses may be presented in a separate report.

11.7. Medical Resource Utilization Analyses

Medical resource utilization will be descriptively summarized by treatment group.

11.8. Safety Analyses

Safety data will be presented descriptively. No statistical testing of safety data is planned. For safety, baseline is defined as the last assessment prior to the first intake of study drug.

The population for the safety analysis will consist of all randomized subjects who received at least one dose of study drug.

Adverse Events

The verbatim terms used in the eCRF by investigators to identify AEs will be coded using the Medical Dictionary for Regulatory Activities. Treatment-emergent AEs are AEs with onset during the treatment phase or that are a consequence of a pre-existing condition that has worsened since baseline. All reported AEs will be included in the analysis. For each AE, the percentage of subjects who experience at least 1 occurrence of the given event will be summarized by treatment group.

Summaries, listings, datasets, or subject narratives may be provided, as appropriate, for those subjects who die, who discontinue treatment due to an AE, or who experience an AE of at least grade 3, or an SAE.

Clinical Laboratory Tests

Laboratory data will be summarized by type of laboratory test and by treatment. Descriptive statistics of absolute values and changes from baseline will be calculated for each laboratory analyte at baseline and at each scheduled time point.

The laboratory abnormalities will be determined according to the criteria specified in the DMID adult toxicity tables (see [Attachment 1](#)) and in accordance with the normal ranges of the clinical laboratory if no gradings are available.

Changes from baseline results will be presented in pre- versus posttreatment cross-tabulations (with classes for below, within, and above normal ranges).

Urinary renal function parameters will be analyzed for the analyte as well as for the analyte ratio over urinary creatinine.

Laboratory abnormalities will be tabulated by scheduled time point.

Electrocardiogram

The effects on cardiovascular variables will be evaluated by means of descriptive statistics and frequency tabulations.

The ECG variables that will be analyzed are heart rate, PR interval, QRS interval, QT interval, and corrected QT (QTc) interval using the following correction methods: QT corrected according to Bazett's formula, and QTcF.^{1,12,14,23}

Descriptive statistics of QTc intervals and changes from baseline will be summarized at each scheduled time point. The percentage of subjects with QTc interval >450 ms, >480 ms, or >500 ms will be summarized, as will the percentage of subjects with QTc interval increases from baseline >30 ms or >60 ms.

All clinically relevant abnormalities in ECG waveform that are changes from the baseline readings will be reported (eg, changes in T-wave morphology or the occurrence of U-waves).

The percentage of subjects with abnormalities (as defined in [Attachment 4](#)) will be tabulated by treatment.

Vital Signs

Descriptive statistics of blood pressure (systolic and diastolic) will be summarized at each scheduled time point. The percentage of subjects with values beyond clinically important limits (as defined in [Attachment 4](#)) will be summarized by treatment.

Physical Examination

Physical examination findings and changes from baseline will be listed at each scheduled time point.

11.9. Data Review Committee

A DRC, comprised of senior sponsor personnel outside of the central sponsor team and not involved in study conduct, will be established. The DRC will monitor safety data during study conduct on a regular basis and/or ad hoc in case of emergent safety signals identified through medical monitoring.

After the review of the accumulating safety data from this study, the DRC will make recommendations regarding the continuation of the study.

The central sponsor team members will review the unblinded interim efficacy, safety, and pharmacokinetic analyses and will make recommendations to the DRC regarding possible changes to the design of the study: dropping the lower dose, changing the stratification factor (and/or the requirement of maximum 50% of all enrolled subjects with symptom onset >3 days before randomization), changing the maximum number of days between RSV symptom onset and randomization and/or the number of time points/visits for collecting a nasal swab by HCP. The DRC will decide on the implementation of the recommendations based on the review of the interim results and other ongoing studies of JNJ-53718678. Given the challenges of ensuring study site preparation in time to recruit for an acute seasonal infection like RSV and the delays caused by implementing an amendment during an RSV season, the changes recommended by the study team and endorsed by the DRC will be communicated in writing to investigators, health authorities, and IECs/IRBs and will be implemented without amendment to this protocol.

Further details of the DRC, eg, composition and activities, will be described in the DRC charter.

12. ADVERSE EVENT REPORTING

Timely, accurate, and complete reporting and analysis of safety information from clinical studies are crucial for the protection of subjects, investigators, and the sponsor, and are mandated by regulatory agencies worldwide. The sponsor has established Standard Operating Procedures in conformity with regulatory requirements worldwide to ensure appropriate reporting of safety information; all clinical studies conducted by the sponsor or its affiliates will be conducted in accordance with those procedures.

Method of Detecting Adverse Events and Serious Adverse Events

Care will be taken not to introduce bias when detecting AEs or SAEs. Open-ended and nonleading verbal questioning of the subject is the preferred method to inquire about AE occurrence.

12.1. Definitions

12.1.1. Adverse Event Definitions and Classifications

Adverse Event

An AE is any untoward medical occurrence in a clinical study subject administered a medicinal (investigational or non-investigational) product. An AE does not necessarily have a causal

relationship with the treatment. An AE can therefore be any unfavorable and unintended sign (including an abnormal finding), symptom, or disease temporally associated with the use of a medicinal (investigational or non-investigational) product, whether or not related to that medicinal (investigational or non-investigational) product. (Definition per International Council for Harmonisation [ICH])

This includes any occurrence that is new in onset or aggravated in severity or frequency from the baseline condition, or abnormal results of diagnostic procedures, including laboratory test abnormalities.

Note: The sponsor collects AEs starting with the signing of the (diagnostic, if applicable) ICF (refer to Section 12.3.1 for time of last AE recording).

Serious Adverse Event

An SAE based on ICH and European Union Guidelines on Pharmacovigilance for Medicinal Products for Human Use is any untoward medical occurrence that at any dose:

- Results in death.
- Is life-threatening.
(The subject was at risk of death at the time of the event. It does not refer to an event that hypothetically might have caused death if it were more severe.)
- Requires inpatient hospitalization or prolongation of existing hospitalization.
- Results in persistent or significant disability/incapacity.
- Is a congenital anomaly/birth defect.
- Is a suspected transmission of any infectious agent via a medicinal product.
- Is medically important*.

*Medical and scientific judgment should be exercised in deciding whether expedited reporting is also appropriate in other situations, such as important medical events that may not be immediately life-threatening or result in death or hospitalization but may jeopardize the subject or may require intervention to prevent one of the other outcomes listed in the definition above. These should usually be considered serious.

If a serious and unexpected AE occurs for which there is evidence suggesting a causal relationship between the study drug and the event (eg, death from anaphylaxis), the event must be reported as a serious and unexpected suspected adverse reaction even if it is a component of the study endpoint (eg, all-cause mortality).

Unlisted (Unexpected) Adverse Event/Reference Safety Information

An AE is considered unlisted if the nature or severity is not consistent with the applicable product reference safety information. For JNJ-53718678, the expectedness of an AE will be determined by whether or not it is listed in the IB.

Adverse Event Associated With the Use of the Drug

An AE is considered associated with the use of the drug if the attribution is possible, probable, or very likely by the definitions listed in Section 12.1.2.

12.1.2. Attribution Definitions

Not Related

An AE that is not related to the use of the drug.

Doubtful

An AE for which an alternative explanation is more likely, eg, concomitant drug(s), concomitant disease(s), or the relationship in time suggests that a causal relationship is unlikely.

Possible

An AE that might be due to the use of the drug. An alternative explanation, eg, concomitant drug(s), concomitant disease(s), is inconclusive. The relationship in time is reasonable; therefore, the causal relationship cannot be excluded.

Probable

An AE that might be due to the use of the drug. The relationship in time is suggestive (eg, confirmed by dechallenge). An alternative explanation is less likely, eg, concomitant drug(s), concomitant disease(s).

Very Likely

An AE that is listed as a possible adverse reaction and cannot be reasonably explained by an alternative explanation, eg, concomitant drug(s), concomitant disease(s). The relationship in time is very suggestive (eg, it is confirmed by dechallenge and rechallenge).

12.1.3. Severity Criteria

An assessment of severity grade will be made using the following general categorical descriptors:

Mild: Awareness of symptoms that are easily tolerated, causing minimal discomfort and not interfering with everyday activities.

Moderate: Sufficient discomfort is present to cause interference with normal activity.

Severe: Extreme distress, causing significant impairment of functioning or incapacitation. Prevents normal everyday activities.

The investigator should use clinical judgment in assessing the severity of events not directly experienced by the subject (eg, laboratory abnormalities).

12.2. Special Reporting Situations

Safety events of interest on a sponsor study drug that may require expedited reporting or safety evaluation include, but are not limited to:

- Overdose of a sponsor study drug.
- Suspected abuse/misuse of a sponsor study drug.
- Accidental or occupational exposure to a sponsor study drug.
- Medication error involving a sponsor product (with or without subject exposure to the sponsor study drug, eg, name confusion).
- Exposure to a sponsor study drug from breastfeeding.

Special reporting situations should be recorded in the eCRF. Any special reporting situation that meets the criteria of an SAE should be recorded on the SAE page of the eCRF.

12.3. Procedures

12.3.1. All Adverse Events

All AEs and special reporting situations, whether serious or non-serious, will be reported from the time a signed and dated ICF is obtained until completion of the subject's last study-related procedure, which may include contact for follow-up of safety. Serious AEs, including those spontaneously reported to the investigator within 30 days after the last dose of study drug, must be reported using the SAE Form. The sponsor will evaluate any safety information that is spontaneously reported by an investigator beyond the time frame specified in the protocol.

All events that meet the definition of an SAE will be reported as SAEs, regardless of whether they are protocol-specific assessments.

Signs and symptoms of RSV disease, such as rhinitis, rhinorrhea, nasal congestion, sneezing, nasopharyngitis, earache, malaise (tiredness), cough, shortness of breath and/or wheezing, muscle and/or joint pain, headache, fever, nasal blood spotting, and decreased oxygen saturation are part of the efficacy-related assessments and hence should not be reported as AEs.

All AEs, regardless of seriousness, severity, or presumed relationship to study drug, must be recorded using medical terminology in the source document and the eCRF. Whenever possible, diagnoses should be given when signs and symptoms are due to a common etiology (eg, cough, runny nose, sneezing, sore throat, and head congestion should be reported as "upper respiratory infection"). Investigators must record in the eCRF their opinion concerning the relationship of the AE to study therapy. All measures required for AE management must be recorded in the source document and reported according to sponsor instructions.

The sponsor assumes responsibility for appropriate reporting of AEs to the regulatory authorities. The sponsor will also report to the investigator (and the head of the investigational institute where required) all suspected unexpected serious adverse reactions (SUSARs). The investigator (or sponsor where required) must report SUSARs to the IEC/IRB that approved the protocol

unless otherwise required and documented by the IEC/IRB. A SUSAR will be reported to regulatory authorities unblinded. Participating investigators and IEC/IRB will receive a blinded SUSAR summary, unless otherwise specified.

For all studies with an outpatient phase, including open-label studies, the subjects must be provided with a "wallet (study) card" and instructed to carry this card with them for the duration of the study indicating the following:

- Study number.
- Statement, in the local language(s), that the subject is participating in a clinical study.
- Investigator's name and 24-hour contact telephone number.
- Local sponsor's name and 24-hour contact telephone number (for medical staff only).
- Site number.
- Subject number.
- Any other information that is required to do an emergency breaking of the blind.

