Furthermore, given that there was an unequal allocation of subjects to JNJ-53718678 and placebo in most studies and that in study 53718678RSV1002 no placebo group was included, the overall number of placebo subjects is low. Hence, this limits the ability to draw firm conclusions on the comparisons made in this section. In addition, most individual AEs and abnormalities were observed at low frequency, which further limits the comparison between JNJ-53718678 and placebo.

During clinical studies 53718678RSV1001, 53718678RSV1002, 53718678RSV1004, and 53718678RSV2001, among subjects who received at least 1 dose of JNJ-53718678, 70% experienced an AE as compared to 46.7% of all subjects who received placebo. All but 1 of the treatment-emergent AEs (TEAEs) reported during these studies were either grade 1 or grade 2 in severity; 1 subject who received placebo was reported with a grade 3 headache in study 53718678RSV1001. Adverse events observed more frequently (difference in incidence of $\geq 5\%$) in subjects who had received at least 1 dose of JNJ-53718678 compared to subjects who received

placebo included diarrhea (20.8% vs 11.1%), dysgeusia (10.8% vs 0.0%), epistaxis (7.5% vs 0.0%), fatigue (6.7% vs 0.0%), abdominal discomfort (5.0% vs 0.0%), and hot flush (5.0% vs 0.0%).

In study 53718678RSV1006, 35.7% and 31.3% of the subjects from Panel 1 and Panel 2, respectively, experienced at least one AE. In this study, all reported AEs were grade 1, and except for abdominal discomfort (reported in 2 subjects [14.3%] in Panel 1), all AEs were reported in at most 1 subject.

In study 53718678RSV1001, dysgeusia was frequently reported in subjects receiving JNJ-53718678 and in none of the subjects of the placebo group. Dysgeusia was a frequently reported AE in subjects receiving JNJ-53718678 due to the bitter taste of the oral JNJ-53718678 formulation. This observation led to the initiation of study 53718678RSV1003 to select an optimized taste of the formulation for future studies.

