Epistaxis as a TEAE was only reported in study 53718678RSV2001, all events were grade 1 in severity, all were considered by the investigator to be not related to the study drug but at least possibly related to RSV, and were reported as recovered prior to the end of the study. The related verbatims included blood stained tissue from nasal mucosa, blood stained nasal wash, blood stained tissue from nasal bleeding, nasal bleeding right/left nostril, and blood spotting nasal wash. Of the 9 subjects who were reported with treatment-emergent epistaxis, 4 were also reported with this AE during the post-challenge phase, 2 during both the pre- and the post-challenge phase, 2 during the treatment phase only, and 1 during both the treatment and the follow-up phase. No association was observed between any of the events and changes in coagulation parameters. While epistaxis as TEAE was not reported in the subjects who received placebo, the observed incidence is consistent with the incidences observed in other RSV challenge studies.^{5,6}

The AE of hot flush was only reported in the MDE part of study 53718678RSV1001 and no dose-related incidence was observed.

In general, none of the reported AEs occurred consistently across different studies and most occurred at a low incidence and low severity. Observed differences in incidence between subjects receiving JNJ-53718678 and those from the placebo group were small for most AEs, considering the limitations of the comparison in view of the difference in sample size of the JNJ-53718678 group and the placebo group. Based upon these AE data, no safety signal was identified for JNJ-53718678.

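### Section 12.3.1 keeps non-serious nasal blood spotting out of the adverse event record as an efficacy item, but no efficacy instrument shown records it

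*Protocol*

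**What the plan says.** Section 12.3.1 defines the exempt group as disease signs, beginning "Signs and symptoms of RSV disease, such as rhinitis, rhinorrhea, nasal congestion, sneezing, nasopharyngitis, earache, malaise (tiredness), cough". The list ends with the instruction that "nasal blood spotting, and decreased oxygen saturation are part of the efficacy-related assessments and hence should not be reported as AEs". The one override in that section is for serious events: "All events that meet the definition of an SAE will be reported as SAEs, regardless of whether they are protocol-specific assessments". There is no exception for signs that start or worsen after the first dose.

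Two other sections describe the same exemption differently. Section 9.2.2 applies it to symptoms reported in the RI-PRO or the RiiQ Symptom Scale. Section 9.7 applies it to evaluations of disease signs and symptoms that belong to the efficacy evaluations. Section 12.1.1 counts as an adverse event any occurrence that is new or aggravated relative to baseline.

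Section 1.1 lists epistaxis among the events at least 5 points more frequent on drug, at 7.5% against 0.0% on placebo. All cases came from challenge study 53718678RSV2001, and the verbatims included "nasal bleeding right/left nostril, and blood spotting nasal wash". The same section adds that "the observed incidence is consistent with the incidences observed in other RSV challenge studies".

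**The concern.** The exemption rests on the premise that the sign is measured elsewhere. If it is not, a non-serious event can fall between the two records: barred from the adverse event page by 12.3.1 and asked about by no questionnaire. It could not be recovered at analysis or pooled with later studies.

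Section 3.2 says that the placebo arm is there so that adverse events can be evaluated properly and drug effects separated from the underlying disease. Section 1.2.4 notes that swabbing can itself cause occasional nose bleeding. With disease, swab and drug all possible causes, and the same swabbing schedule in every arm, a count by arm is the natural way to tell them apart. The exemption removes part of that count for a type of event with an earlier drug-placebo difference.

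**Working it through.** **Step 1: where nasal bleeding could be recorded.**

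| Source | Nasal bleeding item? |
|---|---|
| RI-PRO (Attachment 2) | No. The nose items cover running, congestion, sinus pressure and sneezing |
| Additional questions (Attachment 3) | No. They cover medication, oxygen, overall severity, activities and general health |
| Clinical parameters (9.2.2) | No. Respiratory rate, heart rate, SpO₂ and temperature |
| RiiQ Symptom Scale (Attachment 7) | Cannot be judged: items not in the copy reviewed. Given only to subjects enrolled after approval of Amendment 1 |
| Adverse event page (12.3.1) | Barred if non-serious and regarded as an RSV sign |

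For subjects enrolled before Amendment 1 the RiiQ row drops out, and no efficacy source shown is left. The protocol does not say how many such subjects there are. By contrast, decreased oxygen saturation, named in the same sentence, is covered by SpO₂.

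**Step 2: the three statements of the rule.** Under 9.2.2 and 9.7, a sign is exempt because an efficacy evaluation holds it. On that reading, spotting that no evaluation holds is not exempt, and under 12.1.1 new spotting is an adverse event. Under 12.3.1 it is exempt by name. A site cannot follow all of these.

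**Step 3: reproduce the earlier rate.**
- Drug-treated adults in five studies: 150 (section 1.1).
- The quoted percentages cover four studies and leave out 53718678RSV1006. Its Panel 1 has 14 subjects (2 subjects = 14.3%; 5/14 = 35.7%). Its Panel 2 fits 16 (5/16 = 31.3%). Total 14 + 16 = 30.
- Denominator: 150 − 30 = 120.
- Epistaxis on drug: 9/120 = 7.5%, as stated. Placebo: 0.0%, as stated.

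All nine were among the 50 drug-treated, RSV-inoculated subjects: 9/50 = 18%.

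**Step 4: what those nine cases were.** "Of the 9 subjects who were reported with treatment-emergent epistaxis", 4 also had it in the post-challenge phase and 2 in both the pre- and post-challenge phases, so 4 + 2 = 6 of 9 were also affected in those phases. The other three had it in the treatment phase only (2) or in treatment and follow-up (1). All events were grade 1, judged unrelated to drug and at least possibly related to RSV, and showed no association with coagulation changes. The section does not say how many of the nine had a blood-spotting verbatim.

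**Step 5: what full recording could show.** Take the two active arms together (50) against placebo (25), with a two-sided Fisher test at 5% as a yardstick only, since 11.8 plans no safety testing. With no cases on placebo, 7 of 50 gives p = 0.088 and 8 of 50 gives p = 0.046, so 8 cases are needed. P(at least 8 of 50) is about 3% at a true rate of 7.5%. At 18% it is about 70%, falling to 48% if the placebo rate is 2% (an assumption).

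**The case against.** The case for leaving the rule alone has several parts, and some of them stand.

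- **The rule is narrow.** It covers signs of RSV disease and names blood spotting, not epistaxis. A nosebleed put down to the swab or the drug is arguably outside it, 9.7 asks for any clinically relevant change to be recorded, and serious events are always reported. This stands as a limit on size. It does not remove the gap, because in an infected patient spotting is readily read as the disease sign that 12.3.1 names.
- **The earlier imbalance is weak evidence of a drug effect.** Step 4 bears this out. Only some of the coded verbatims were spotting, and some came from nasal washes, whereas this trial uses swabs. A reader might apply 7.5% or 18% to the 50 active subjects here and forecast a number of lost events. The documents do not support that: the sampling differs and the share described as spotting is unknown.
- **Sample size, not the rule, limits the answer.** A reader might infer that the exemption is why this trial cannot confirm or clear the imbalance. At the pooled rate of 7.5%, about 3% power with full recording shows otherwise. What the rule costs is part of the descriptive record.
- **Tiredness.** It is on the same exempt list, and fatigue also appears among the earlier imbalances (6.7% vs 0.0%), so a reader might extend the point to it. That fails. The RI-PRO has an item for being weak or tired, and 11.4.2 summarises all questionnaire data by arm. After Amendment 1 the RI-PRO is scheduled only at screening, Day 1 before dosing and Day 8, but the RiiQ is then added and its items cannot be judged here.
- **Exempting endpoint symptoms is ordinary practice in infected patients.** Agreed, where the symptom is measured as an endpoint. For blood spotting, no measurement is shown.

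**Conclusion.** The point holds for one term. Section 12.3.1 calls nasal blood spotting efficacy-assessed, no efficacy instrument shown assesses it, and 9.2.2 and 9.7 tie the exemption to what is assessed. Non-serious events of this type, which were among those coded as epistaxis before (9/120 = 7.5% vs 0.0%), could be missing from the by-arm safety tables.

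The consequence is modest. The earlier events were all grade 1 and judged unrelated to drug, and the safety analysis is descriptive. No count of lost events can be given. The conclusion assumes that sites apply 12.3.1 as written and regard spotting as an RSV sign. If the RiiQ Symptom Scale contains a nasal bleeding item, the gap shrinks to subjects enrolled before Amendment 1.

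**What to change.** Delete nasal blood spotting from the exempt list in 12.3.1, or keep it exempt only when it was present before the first dose and does not worsen. State that nasal bleeding which starts or worsens after the first dose is recorded as an adverse event and tabulated by arm, and bring the wording of 9.2.2, 9.7 and 12.3.1 into line.

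The cost is one sentence in 12.3.1, matching site guidance and a few extra low-grade entries, many of them due to swabbing or the infection itself. No study procedure or visit changes.
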